1.5.2 Safety

The assessment of safety was based mainly on the frequency of adverse events and on the number of laboratory values that fall outside of pre-determined ranges. Other safety data (e.g. electrocardiogram, vital signs, and special tests) were considered as appropriate.

1.5.2.1 Adverse events

Adverse events (AE) were summarized by presenting the number and percentage of patients having any adverse event, having an adverse event in each body system and having each individual adverse event. Furthermore, the incidence of AE was summarized by maximum severity, for AE with suspected drug relation, for serious AE, for AE leading to permanent discontinuation of study drug, and for significant AE. As significant (S)AE were defined those (S)AE who

- were suspected to be drug related,
- lead to dose adjustment or temporary interruption,
- lead to permanent discontinuation,
- required concomitant medication/non-drug therapy, and
- Deaths

Any other information collected (e.g. severity or relatedness to study medication) was listed as appropriate.

1.5.2.2 Laboratory values

Laboratory data were summarized by presenting summary statistics of raw data and changes from baseline value by visit. Although foreseen in the protocol, notable values were not analyzed since no notable ranges were defined in the protocol. Any statistical tests performed to explore the data were used only to highlight any interesting comparisons that may warrant further consideration.

Data from other tests (e.g. electrocardiogram or vital signs) were planned to be listed, notable values were recommended to be flagged (if appropriate), and any other information collected was planned to be listed as appropriate.

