6.3.2 RAD001 dose adjustments

For patients who are unable to tolerate the protocol-specified RAD001 dosing schedule, dose-adjustment guidelines are given below. Three RAD001 dose levels are defined for dose adjustment: 10mg daily, 5mg daily, and 5mg every other day. (Table – 1)

Table 6-1 RAD001 Dose levels for dose adjustment

Dose level	Dose and schedule
0 (starting dose)	10mg daily
Decrease 1 dose level	5mg daily
Decrease 2 dose levels	5mg every other day

Toxicity will be assessed using the NCI-CTC for Adverse Events, version 3.0 (CTCAE v3.0,

(<http://ctep.cancer.gov/forms/CTCAEv3.pdf>).

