10.5.2.2 Laboratory values

Laboratory data will be summarized by presenting shift tables using extended normal ranges (baseline to most extreme post-baseline value), by presenting summary statistics of raw data and change from baseline values (means, medians, standard deviations, ranges) and by the flagging of notable values in data listings.

Data from other tests (e.g. electrocardiogram or vital signs) will be listed, notable values will be flagged, and any other information collected will be listed as appropriate. Any statistical tests performed to explore the data will be used only to highlight any interesting comparisons that may warrant further consideration.

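### The SAP names out-of-range laboratory values as a main safety basis but plans no laboratory table that counts the patients affected, and it omits the protocol's shift tables without listing the change

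*SAP*

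**What the plan says.** SAP 1.5.2 states that safety is "based mainly on the frequency of adverse events and on the number of laboratory values that fall outside of pre-determined ranges". Protocol 10.5.2 has the same two-part basis.

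Protocol 10.5.2.2 planned three laboratory outputs. The first is described as follows: "Laboratory data will be summarized by presenting shift tables using extended normal ranges (baseline to most extreme post-baseline value"). The second is summary statistics of raw and change values. The third displays abnormal values "by the flagging of notable values in data listings".

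SAP 1.5.2.2 keeps the second: "Laboratory data were summarized by presenting summary statistics of raw data and changes from baseline value by visit". It drops the third openly, on the ground that "notable values were not analyzed since no notable ranges were defined in the protocol". It does not mention the first. The list of changes from the protocol in SAP Section 1 has two items, local instead of central tumor assessment and the ITT set instead of the PP set for the primary analysis. Neither concerns laboratory data.

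**The concern.** The SAP promises a count in one subsection and provides no means of producing it in the next. Protocol 6.3.3 names neutropenia, thrombocytopenia and raised cholesterol or triglycerides as the most frequent laboratory abnormalities with this drug, and it notes that grade 3 hyperglycemia has been seen. For such effects a reader of a phase II report wants to know how many patients worsened, from what starting point and to what grade. Tolerability and safety form a secondary objective in each arm (Protocol Section 3).

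The record of changes also matters. SAP 1.5.1 remarks that no patient reached a best overall response of CR or PR, so at least some outcomes were known when the text was written. Departures from the protocol should then be listed in full.

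**Working it through.** No sample size, power or alpha figure is involved. The check is a comparison of texts, followed by a look at what the retained statistics can and cannot show.

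**1. Planned against retained.**

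| Output in Protocol 10.5.2.2 | SAP 1.5.2.2 | In the SAP Section 1 list of changes? |
|---|---|---|
| Shift tables, baseline to worst value | Not mentioned | No |
| Summary statistics, raw and change | Kept, by visit | Not a change |
| Notable values flagged in listings | Dropped, reason given | No |

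**2. Does the stated reason cover the shift tables?** The reason concerns notable ranges. The protocol's shift tables were to use extended normal ranges, a different term. The protocol defines neither, so a similar reason could have been offered for the shift tables, but the SAP does not offer one.

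**3. Were usable limits available?** Yes.
- Protocol 6.3.2 states: "Toxicity will be assessed using the NCI-CTC for Adverse Events, version 3.0". Protocol 7.5.1 uses the same scale for adverse events.
- Protocol Table 6-2 prints platelet limits (grade 3 below 50, grade 4 below 25 x10^9/L) and neutrophil limits (grade 3 below 1, grade 4 below 0.5 x10^9/L).
- Protocol 6.3.3 prints grade 2 limits for cholesterol (above 300 mg/dL) and triglycerides (above 2.5 x ULN).
- Protocol 7.5.5 requires each site to supply its laboratory normal ranges.

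**4. What do the retained statistics show?** SAP Section 1 defines them as N, N missing, mean, SD, median, minimum and maximum. Suppose, as an assumption, that the lowest platelet count at a visit is 20 x10^9/L, below the grade 4 limit of 25. The minimum column prints 20, so the event is visible. The minimum is the same 20 whether one patient or several are at that level:
- Planned 36 patients (arm I): 1/36 = 2.8% or 2/36 = 5.6%.
- Planned 24 patients (arm II): 1/24 = 4.2% or 2/24 = 8.3%.
- 8 enrolled patients (arm III, Protocol Section 10): 1/8 = 12.5% or 2/8 = 25%.

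If low minima appear at two visits, the tables do not say whether they belong to the same patient. They also do not link a low value to that patient's baseline. A baseline-to-worst table answers all three questions.

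**5. Do the adverse event tables fill the gap?** In part. Under Protocol 7.5.1 a laboratory abnormality becomes an adverse event if it causes signs or symptoms, is judged clinically significant or needs therapy. It is also recorded if it leads to study discontinuation or is itself serious. Dose interruption is not a listed trigger. A grade 3 neutropenia that is asymptomatic and untreated calls for interruption under Table 6-2, yet it enters the adverse event tables only if the investigator judges it clinically significant.

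**The case against.** The case on the other side has real weight.

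- **Adverse events come first.** SAP 1.5.2 names their frequency before laboratory counts. A reader might infer that safety rests mainly on laboratory data; the text does not say so.
- **More than means are kept.** A reader might infer that only averages remain and that individual toxicity is invisible. The SAP's own definition of summary statistics includes minimum and maximum, so an extreme value appears at its visit. What is lost is the number of patients, not every sign of a problem.
- **Other tables catch much of it.** Protocol 6.3.3 directs lipid-lowering treatment from grade 2, and a treated abnormality is an adverse event by definition. SAP 1.5.2.1 tabulates adverse events by maximum severity, by discontinuation, and as significant events that include those leading to dose adjustment or interruption. SAP 1.3 tabulates dose changes by reason.
- **The stated reason is literally true.** The protocol defines no notable ranges, it planned notable values only as flags in listings, and the SAP discloses dropping them.
- **Laboratory safety is descriptive.** No hypothesis or decision rule depends on it.

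These points limit the concern but do not remove it. Dose-change tables do not give graded laboratory incidence. Abnormalities that are untreated and without symptoms can still go uncounted. None of the points explains the missing shift tables or supplies the count that SAP 1.5.2 relies on.

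**Conclusion.** The inconsistency stands. Followed as written, the SAP yields no laboratory table of how many patients had out-of-range or worsening values, although it names a count of such values as one of two main safety bases. The shift tables are omitted with neither a reason nor an entry in the list of changes.

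The effect is confined to safety reporting, in all three arms. How many patients would be missed cannot be computed from the documents, since it depends on how often investigators report laboratory findings as adverse events. A reader might infer that the tables were dropped to hide toxicity. Nothing in the documents supports that: the notable-value decision is disclosed, and extreme values stay visible.

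Two assumptions apply. The shift tables are taken to have been in the protocol when the SAP was written. The SAP's remark that notable values were foreseen there fits this, since both stand in the same sentence of Protocol 10.5.2.2. Counts made outside the SAP, if any, are unknown.

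**What to change.** Amend SAP 1.5.2.2 as follows.

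1. On the safety set and for each arm, present shift tables from baseline to worst post-baseline CTCAE v3.0 grade for every graded parameter, with the number and percentage of patients at grade 3-4.
2. For parameters without a CTCAE grade, use the site normal ranges already collected (low, normal, high).
3. In the SAP Section 1 list of changes, record that notable-value flagging was dropped and that CTCAE grades or site ranges replace the undefined extended normal ranges.

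If the sponsor decides against the tables, the minimum is to remove the laboratory count from the stated basis in SAP 1.5.2 and to list the omission of the shift tables as a change.

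The cost is a few standard tables and some programming. Protocol 7.5.5 lets sites report differentials as percentages or absolute values, so some neutrophil counts must be derived as total white cells x percentage / 100. The total white cell count is in the same panel, so no new data are needed.

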1.5.3 Tolerability

Not applicable.

1.5.4 Resource utilization

Not applicable.

1.6 Sample size calculation

The study followed an exact binomial single-stage design in each arm. (A'Hern 2001). Values of P_0 and P_1 followed the recommendation of the EORTC Soft Tissue and Bone Sarcoma Group's previous publication evaluating PFS in STS patients treated with 2nd line active and inactive compounds.

In arm I (patients with bone and soft tissue sarcoma except for GIST), the study required 36 evaluable subjects to decide whether the proportion responding (best overall response of CR, PR or SD), p , was less than or equal to $p_0 = 20\%$ or greater than or equal to $p_1 = 40\%$ (Table 10-1). In arm II or III (patients with GIST after failure or intolerance of 1st and 2nd line treatment with imatinib or sunitinib, and patients with progressive or metastatic alveolar soft part sarcoma (ASPS), respectively), the study required 24 evaluable subjects to decide whether the proportion responding best overall response of CR, PR or SD), p , was less than or equal to $p_0 = 20\%$ or greater than or equal to $p_1 = 40\%$.

If the number of responses in arm I was 11 or more, the null hypothesis that p is less than or equal to 20% was to be rejected with a target type I error rate of 10% and an actual error rate of 8.9%. If the number of responses in arm I was 10 or less, the alternative hypothesis that p is greater than or equal to 40% was to be rejected with a target type II error rate of 10% and an actual error rate of 9%.

If the number of responses in arm II or arm III, respectively, was 8 or more, the null hypothesis that p is less than or equal to 20% was to be rejected with a target type I error rate of 10% and an actual error rate of 8.9%. If the number of responses in arm II was 7 or less, the alternative hypothesis that p is greater than or equal to 40% was to be rejected with a target type II error of 20% and an actual error rate of 19.2%.

The designs were estimated with NCSS Trial and PASS 2002.

Table 10-1 Design features for exact binomial single-stage designs

	Arm I	Arm II	Arm III
p_0 (maximum response proportion of an inactive drug)	20%	20%	20%
p_1 (minimum response proportion of an active drug)	40%	40%	40%
Type I error (one-sided test)	10%	10%	10%
Type II error (one-sided test)	10%	20%	20%
Sample size	36	24	24
Accept inactivity at the end if	≤ 10 responders	≤ 7 responders	≤ 7 responders
Reject inactivity at the end if	≥ 11 responders	≥ 8 responders	≥ 8 responders
Actual type I error level	8.9%	8.9%	8.9%
Actual type II error level	9.0%	19.2%	19.2%

The type I error is the probability of rejecting the hypothesis that p is lower or equal to p_0 when this is true. **The type II error** is the probability of rejecting the hypothesis that p is greater or equal to p_1 when this is true. Response was defined as a best overall response of CR, PR or SD.

1.7 Power for analysis of critical secondary variables

Not applicable.
